9.6 Pharmacodynamics

Refer to Section 9.8.

9.8 Biomarkers

Thrombus formation will be determined using the Badimon chamber. Venous blood will be collected from study participants through a cannula set attached to extension tubing. The tubing will be connected to a series of 3 perfusion chambers containing porcine aorta as a thrombogenic surface. A pump placed distal to the chambers will maintain unidirectional flow at a rate of 10 mL/min. The rheologic conditions in the first chamber stimulate those of patent arteries (low shear rate, approximately 212 s^{-1}), and those in the second and third chambers simulate those of stenosed arteries (high shear rate, approximately 1690 s^{-1}). Each perfusion study will last for 5 minutes. Immediately after each perfusion, porcine strips with thrombus attached will be

removed and fixed, and total thrombus area will be assessed by morphometrical analysis.

Aortic strip analysis will be performed blinded. Aortic strips will be assigned and stored with a unique sample number unrelated to the participant number. Aortic stripes are then processed by the histology department, who are blinded to the study entirely, and analyzed at a later date by an operator blinded to the aortic strip linked sample numbers. Sample linkage will be kept securely in the study site.

Circulating biomarker assessment for this chamber study focuses primarily on PD biomarkers.

In addition, serum samples will be collected for assessment of SARS-CoV-2 serology.

Blood will be drawn at the times indicated in Table 9.8-1 and [Table 9.8-2](#). Further details of blood collection and processing will be provided to the site in the procedure manual.

Table 9.8-1: Biomarker Sampling Schedule - Treatment Arms 1, 2, and 3

Study Day of Sample Collection	Event	Time (Relative To BMS-986141 Dose) Hour:Min				Serum for SARS-CoV-2 serology
1	predose	-02:00				X
1		02:00				
2		24:00				

Abbreviations:

Table 9.8-2: Biomarker Sampling Schedule - Treatment Arm 4

Study Day of Sample Collection	Event	Time (Relative To BMS-986141 Dose) Hour:Min	■■■■■	■■■■■	■■■■■	Serum for SARS-CoV-2 serology
1	predose	00:00	■	■	■	X
1		02:00	■	■	■	
2		24:00	■	■	■	

Abbreviations: ■■■■■ = [REDACTED]

9.8.1 Additional Research Collection

This protocol will include residual sample storage.

For All US Sites:

Not applicable.

For non-US Sites

Additional research is optional for all study participants, except where retention and/or collection is prohibited by local laws or regulations, ethics committees, or institutional requirements.

This collection for additional research is intended to expand the translational R&D capability at Bristol-Myers Squibb, and will support as yet undefined research aims that will advance our understanding of disease and options for treatment. It may also be used to support health authority requests for analysis, and advancement of pharmacodiagnostic development to better target drugs to the right patients. This may also include genetic/genomic exploration aimed at exploring disease pathways, progression and response to treatment etc.

Sample Collection and Storage

All requests for access to samples or data for additional research will be vetted through a diverse committee of the study sponsor's senior leaders in Research and Development (or designee) to ensure the research supports appropriate and well-defined scientific research activities.

[REDACTED] biomarker, and [REDACTED] (see Table 9.8.1-1) will also be retained for additional research purposes.

Samples kept for future research will be stored at the [REDACTED] or an independent, BMS-approved storage vendor.

The manager of these samples will ensure they are properly used throughout their usable life and will destroy the samples at the end of the scheduled storage period, no longer than fifteen (15) years after the end of the study or the maximum allowed by applicable law.

Transfers of samples by research sponsor to third parties will be subject to the recipient's agreement to establish similar storage procedures.

Samples will be stored in a coded fashion, and no researcher will have access to the key. The key is securely held by the Investigator at the clinical site, so there is no direct ability for a researcher to connect a sample to a specific individual.

Further details of sample collection and processing will be provided to the site in the procedure manual.

Table 9.8.1-1: Residual Sample Retention for Additional Research Schedule

Sample Type	Time Points for Which Residual Samples Will be Retained
Plasma PK	All
Whole blood/DNA	All
Plasma serum biomarkers	All

Abbreviation: PK = pharmacokinetic

9.8.2 Other Assessments

Not applicable.

9.9 Health Economics OR Medical Resource Utilization and Health Economics

Health Economics/Medical Resource Utilization and Health Economics parameters will not be evaluated in this study.

10 STATISTICAL CONSIDERATIONS

10.1 Sample Size Determination

The sample size for this study is not based on statistical power, but based on consideration of the precision of the estimate of the effect of BMS-986141 alone and as add on to aspirin, ticagrelor, or the aspirin/ticagrelor combination, on thrombus formation in an ex vivo porcine aortic thrombosis chamber model as compared to pretreatment.

The half-width of the 95% CI of the change from baseline in thrombus area on the log scale after administration of BMS-986141 will be 0.146 or 0.188 if there are 15 or 10 participants per arm, respectively. This calculation assumes that the thrombus area is log-normally distributed and the change from baseline on the log scale has a standard deviation of 0.263 as observed in CV004-007.

The following table provides examples of 95% CIs of the true percent reduction in thrombus area after administration of BMS-986141, assuming the true percent reduction (percent decrease from baseline) is 15%, 20%, or 30%, and the sample size is 15 per arm or 10 per arm.

Sample Size per Arm	True Reduction from Baseline	Change from Baseline on Log Scale (95% CI)	Geometric Mean Ratio to Baseline (95% CI)
15	15%	-0.163 (-0.309, -0.017)	0.85 (0.73, 0.98)
15	20%	-0.223 (-0.369, -0.077)	0.80 (0.69, 0.93)
15	30%	-0.357 (-0.503, -0.211)	0.70 (0.60, 0.81)
10	30%	-0.357 (-0.545, -0.169)	0.70 (0.58, 0.84)

Approximately 55 participants (15 participants in Treatment Arms 1, 2, and 3, and 10 participants in Treatment Arm 4) are planned to be dosed with BMS-986141.

10.2 Populations for Analyses

For purposes of analysis, the following populations are defined:

Population	Description
Enrolled	All participants who sign informed consent
Treated	The Treated Population is a subset of the Enrolled Population including all participants who received BMS-986141.
Pharmacokinetic	The PK Population is a subset of the Treated Population. The PK Population includes all participants who received BMS-986141 and had any available concentration-time data
Biomarker	The Biomarker Population is a subset of the Treated Population. The Biomarker Population includes all participants who received BMS-986141 and had any available biomarker data.

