Ticagrelor BID, Aspirin, or Ticagrelor BID/Aspirin Administration		X	Participants who are not previously taking ticagrelor BID, aspirin, or ticagrelor BID + aspirin will be required to take 1 of the medications for at least 7 days prior to Day 1 to ensure steady state has been attained. This is not required for healthy participants enrolled in Treatment Arm 4.
Adverse Event Reporting			
Monitor for Non-Serious Adverse Events		X	Collected only for participants who participate in the Run-in Period.
Monitor for SAEs	X	X	All SAEs must be collected from the date of participant's written consent until 30 days after the last dose of study treatment or participant's participation in the study.

Abbreviations: BID = twice daily; HIV = human immunodeficiency virus; SAE = serious adverse event; WOCBP = women of childbearing potential

Table 2-2: On Treatment Procedural Outline (CV006037) - Treatment Arms 1, 2, and 3

Procedure	Day 1 (Visit 1)	Day 2 (Visit 2/Clinic Discharge ^a)	Day 8/ Study Discharge	Notes
Check-in Assessments				
Inclusion/Exclusion Criteria	X			
Medical History	X			Interim medical history collected before dosing on Day 1. Include any toxicities or allergy related to previous treatments.
Prior Medication Use	X			History of prior medications will be assessed before dosing on Day 1.
Report to Study Site	X	X		In the morning on Day 1, participants will report to the study site prior to the baseline chamber run. Participants will be released from the clinic after the Hour 2 chamber run is complete and the PK sample is collected. Participants will return to the study site approximately 1 hour before the final chamber run on Day 2.
Safety Assessments				
Physical Examination	X	X		If the screening physical examination is performed within 24 hours prior to dosing on Day 1, then a single exam may count as both the screening and predose evaluation. Physical examinations will be performed at check-in (if the screening physical examination is performed more than 24 hours prior to dosing on Day 1) and after the chamber run on Day 2. Standard baseline photographs of any area with clinical findings will be taken. See Section 9.4.1.1
Physical Measurements	X	X		Weight only at check-in and Day 2. Body mass index will be calculated before dosing on Day 1.
Vital Signs	X	X		See note in screening procedures. Vital signs will be obtained at check-in and prior to and after each chamber assessment on Days 1 and 2.

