The primary objective of this study is to assess the effect of BMS-986141 on thrombus formation in an ex-vivo porcine aortic thrombosis chamber model. Key secondary objectives are to assess the safety and tolerability of BMS-986141 when given with aspirin, ticagrelor, or with aspirin and ticagrelor in participants with coronary artery disease; to assess the safety of aspirin alone, ticagrelor alone, and the combination of aspirin and ticagrelor in participants with coronary artery disease; and to assess the safety and tolerability of a single dose of BMS-986141 in normal healthy participants.

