5 STUDY DESIGN

5.1 Overall Design

This is an open-label, single-center, 4-arm study to assess the effect of BMS-986141 on thrombus formation in an ex vivo porcine aortic thrombosis chamber model as compared to pretreatment with BMS-986141. Participants will be screened to determine eligibility within 28 days prior to study treatment.

An optional Run-in Period will take place after screening if participants are taking a similar antiplatelet drug (eg, clopidogrel), a lower dose of ticagrelor twice daily (BID), aspirin, or ticagrelor BID + aspirin or are not currently taking ticagrelor BID, aspirin, or ticagrelor BID + aspirin as part of their standard of care. Participants will receive ticagrelor BID, aspirin, or ticagrelor BID + aspirin daily for at least 7 days under the supervision of the investigator prior to Day 1. The timing of each dose and number of tablets taken will be recorded in a diary. Diaries will be reviewed by study site personnel on Day 1. Participants who do not have 100% compliance will not continue in the study. Participants who do not currently receive any antiplatelet therapy, or who are currently on aspirin alone as their standard of care, will be excluded from Treatment Arm 3 (triple therapy).

Approximately 15 participants each with a confirmed history of (must have at least 1 of the following conditions) proven coronary artery disease (greater than 50% stenosis of proximal coronary artery), prior coronary revascularisation (percutaneous coronary intervention or coronary artery bypass grafting), and/or prior myocardial infarction will be enrolled to 1 of 3 treatment arms

(15 participants per arm, based on their background therapy). Treatment arms will not be randomized but instead be allocated as open-label at the discretion of the Principal Investigator as shown below. Enrollment will require that Treatment Arms 1-3 shall enroll 15 participants each while Treatment Arm 4 (healthy volunteers) will enroll 10 participants.

- Treatment Arm 1: Single oral dose of 90 mg ticagrelor alone, followed by a single oral dose of 4 mg BMS-986141 approximately 2 hours later (Day 1). A second dose of ticagrelor will be taken approximately 12 hours after the first dose. Twice daily dosing of ticagrelor will be continued on Day 2.
- Treatment Arm 2: Single oral dose of 75 mg aspirin alone, followed by a single oral dose of 4 mg BMS-986141 approximately 2 hours later (Day 1). Daily dosing of aspirin will continue on Day 2.

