6.4 Screen Failures

Screen failures are defined as participants who consent to participate in the clinical study but who are not subsequently entered in the study/included in the analysis population. A minimal set of screen failure information is required to ensure transparent reporting of screen failure participants, to meet the Consolidated Standards of Reporting Trials (CONSORT) publishing requirements, as applicable, and to respond to queries from regulatory authorities. Minimal information includes date of consent, demography, screen failure details, eligibility criteria, and any serious AEs (SAEs).

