7 TREATMENT

Study treatment is defined as any investigational treatment(s), marketed product(s), placebo, or medical device intended to be administered to a study participant according to the study allocation.

Study treatment includes both Investigational [Medicinal] Product (IP/IMP) and Non-investigational [Medicinal] Product (Non-IP/Non-IMP) and can consist of the following:

- BMS-986141 oral tablets at a dose of 4 mg (IP)
- Ticagrelor oral tablets at a dose of 90 mg BID (IP)
- Aspirin oral tablets at a dose of 75 mg (IP)

An IP, also known as IMP in some regions, is defined as a pharmaceutical form of an active substance or placebo being tested or used as a reference in a clinical study, including products already with a marketing authorization but used or assembled (formulated or packaged) differently

than the authorized form, or used for an unauthorized indication, or when used to gain further information about the authorized form.

The study treatments for this study are presented in [Table 7-1](#). Instructions for storage and administration will be provided to the investigative site separate from the protocol.

The investigator will source, purchase, and provide sufficient marketed product of ticagrelor 90-mg tablets and aspirin 75-mg tablets.

Other medications used as support or escape medication for preventative, diagnostic, or therapeutic reasons, as components of the standard of care for a given diagnosis, may be considered as non-IPs.

Table 7-1: Study Treatments for CV006037

Product Description / Class and Dosage Form	Potency	IP/Non-IMP	Blinded or Open Label	Packaging / Appearance	Storage Conditions (per label)
BMS-986141 tablets	4 mg	IP	Open label	Tablets in HDPE containers	Refer to labeled instructions
Ticagrelor ^a	90 mg	IP	Open label	Tablets in commercial packaging	Refer to SmPC
Aspirin ^a	75 mg	IP	Open label	Tablets in commercial packaging	Refer to SmPC

^a Ticagrelor and aspirin will be sourced by the study investigator and not provided by BMS as local commercial product. Storage should be in accordance with the package insert or summary of product characteristics (SmPC)

Abbreviations: HDPE = high-density polyethylene; IP = investigational product; SmPC = summary of product characteristics

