Starting on Day 1, standard baseline photographs of any area with clinical findings will be taken at the discretion of the Principle Investigator. If there are any changes with the affected areas or new clinical findings, additional photographs will be obtained. Photographs will not be needed if there is no clinical finding or no change in the affected areas.

9.4.2 *Vital signs*

Refer to Schedule of Activities (Section 2).

9.4.3 *Electrocardiograms*

Refer to Schedule of Activities ([Section 2](#)).

9.4.4 *Clinical Safety Laboratory Assessments*

- Investigators must document their review of each laboratory safety report.
- A local laboratory will perform the analyses and will provide reference ranges for these tests.
- Results of clinical laboratory tests performed on Day 1 must be available prior to BMS-986141 dosing.

Hematology	
Red blood cells	
Hemoglobin	
Hematocrit	
Total leukocyte count, including differential	
Platelet count	
Chemistry	
AST	Total protein
ALT	Albumin
Total bilirubin	Sodium
Direct bilirubin	Potassium
Alkaline phosphatase	Chloride
Lactate dehydrogenase	Calcium
Creatinine	Phosphorus
Blood urea nitrogen	Magnesium
Uric acid	Creatine kinase
Fasting glucose	
Coagulation	
INR	
aPTT	
Prothrombin time	
Platelet count	
Urinalysis	
Protein	
Glucose	
Blood	
Leukocyte esterase	
Specific gravity	
pH	
Microscopic examination of the sediment if blood, protein or leukocytes esterase are positive on the dipstick	
Serology	

Serum for hepatitis C antibody, hepatitis B surface antigen, HIV-1 and -2 antibodies (screening only). See [Appendix 7](#) for hepatitis B serologic test results interpretation.

Other Analyses

Test for drugs of abuse and alcohol (urine or serum) (screening and Day 1)

Pregnancy test (WOCBP only: screening, predose, clinic discharge)

Follicle-stimulating hormone (postmenopausal women only; screening)

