10.3.2 Safety Analyses

All safety analyses will be performed on the Treated Population.

Endpoint	Statistical Analysis Methods
Secondary: AEs, clinical laboratory	Descriptive summaries will be presented for continuous variables using number of participants (N), mean, standard deviation, median, minimum, and maximum. Descriptive summaries for categorical variables will utilize counts

values, vital signs, ECGs, or other safety biomarkers	and percentages. All recorded AEs will be listed and tabulated by system organ class, preferred term, treatment arm, and treatment. Vital signs, ECGs, and clinical laboratory test results will be listed and summarized by planned time point, treatment arm, and treatment. Marked abnormal clinical laboratory test results will be summarized by treatment arm and treatment. Any significant physical examination findings will be listed. Electrocardiogram readings will be summarized by planned time point, treatment arm, and treatment, and investigator-identified abnormalities, if present, will be listed.
---	--

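### The safety population requires receipt of BMS-986141, so participants who take study ticagrelor or aspirin and leave before it are missing from the safety summaries of those drugs

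*Combined protocol and SAP*

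**What the plan says.** Section 10.2 defines four sets. Enrolled is everyone who consents. For the second it says: "The Treated Population is a subset of the Enrolled Population including all participants who received BMS-986141". The PK and Biomarker sets are subsets of Treated. No set is defined by receipt of any study drug.

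Section 10.3.2 then states: "All safety analyses will be performed on the Treated Population". It gives no exception.

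Among the key secondary objectives, section 3.1 includes "to assess the safety of aspirin alone, ticagrelor alone, and the combination of aspirin and ticagrelor in participants with coronary artery disease", and Table 4-1 carries the same objective with AEs, laboratory values, vital signs and ECGs as endpoints. Section 7 lists ticagrelor and aspirin, like BMS-986141, as investigational product.

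Section 5.1 provides a run-in of at least 7 days on the background drug for those who need it. Of those whose diary shows any shortfall it says: "Participants who do not have 100% compliance will not continue in the study". Table 2-1 schedules non-serious AE monitoring in this period, with the note "Collected only for participants who participate in the Run-in Period". On Day 1 the background dose precedes BMS-986141 by about 2 hours, and the baseline chamber run falls between the two.

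**The concern.** For the background-therapy objective, the relevant exposure is a dose of ticagrelor or aspirin. The plan instead makes inclusion depend on a later event, receipt of a different drug. A participant who takes study ticagrelor or aspirin, has an adverse event and leaves before BMS-986141 is missing from both the numerator and the denominator of the summary meant to describe that drug.

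The exclusion can be tied to the outcome itself. Eligibility is rechecked on Day 1 (Table 2-2), current or recent bleeding is an exclusion (section 6.2), and section 8.1 requires investigational product to be stopped for specified bleeding. A bleed during the run-in could therefore remove someone before they count as Treated. If early exits reflect tolerability, background therapy will look better tolerated than it was. Whether they do cannot be told from the documents, since a missed dose can have other causes.

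**Working it through.** **Comparing the rules**

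| Element | Where | Content |
|---|---|---|
| Objective | 3.1, Table 4-1 | Safety of ticagrelor, aspirin and the combination in coronary patients |
| Status of these drugs | 7 | Investigational product |
| First in-study exposure | 5.1 | Run-in (at least 7 days) where it applies; otherwise the Day 1 dose about 2 hours before BMS-986141 |
| Entry to the safety set | 10.2, 10.3.2 | Receipt of BMS-986141 |

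Two routes lead from exposure to exclusion.

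1. *Run-in.* Dosing is supervised and non-serious AEs are collected, but anyone below 100% compliance is removed before Day 1 dosing.
2. *Day 1.* A participant may leave after the background dose, for instance around the baseline chamber run. Section 9.4.4 adds: "Results of clinical laboratory tests performed on Day 1 must be available prior to BMS-986141 dosing". It does not require those results before the background dose.

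Section 10.3.2 tabulates AEs by arm and by treatment, and Table 7.1-1 lists the background regimens as treatments separate from BMS-986141. A table for a background regimen would therefore omit some of its recipients.

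**Size**

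The plan gives no figure on this point: no run-in entry rate, dropout rate or AE rate. The only input is the planned number dosed, 15 in each of Arms 1 to 3 (section 10.1). Everything else below is assumed.

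Let *a* of the 15 dosed have an event on background drug, and let *k* further participants leave before BMS-986141, *e* of them with an event. The plan reports a/15. The proportion among all exposed is (a + e)/(15 + k).

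With every early leaver having an event (e = k), and exact (Clopper-Pearson) 95% CIs for a = 0:

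| k | a = 0: plan | a = 0: all exposed | a = 1: plan | a = 1: all exposed |
|---|---|---|---|---|
| 0 | 0/15 = 0% (0 to 21.8%) | same | 1/15 = 6.7% | same |
| 1 | 0/15 = 0% | 1/16 = 6.25% (0.2 to 30.2%) | 1/15 = 6.7% | 2/16 = 12.5% |
| 3 | 0/15 = 0% | 3/18 = 16.7% (3.6 to 41.4%) | 1/15 = 6.7% | 4/18 = 22.2% |

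The plan understates the proportion only when e/k exceeds a/15. With a = 1 and three leavers without events, all exposed gives 1/18 = 5.6% against the plan's 6.7%, so the direction can reverse.

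The run-in is optional, so its own denominator may be smaller than 15. If 5 or 10 of the 15 dosed came through it without an event, one excluded event gives 1/(5 + 1) = 16.7% (0.4 to 64.1%) or 1/(10 + 1) = 9.1% (0.2 to 41.3%). A pooled arm denominator would show 1/16 = 6.25%.

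**The case against.** The strongest objection is that the run-in is not part of the treatment under study. It appears in the screening table, its stated purpose is to reach steady state, section 5.3 separates screening from treatment, and Table 7.1-1 lists background doses on Days 1 and 2 only. On that reading a non-complier is a pretreatment failure. This shows that the protocol is unclear about run-in doses. It does not settle the matter, because the drugs are investigational product, dosing is under investigator supervision, and non-serious AEs are collected there. The Day 1 route remains on either reading.

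That route is narrow, however. The window is about 2 hours, in people required to have taken 7 consecutive days of the drug. The Day 1 laboratory samples are drawn at check-in, and the documents do not place them before or after the background dose. This limits the numbers but does not close the route.

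Section 10.3.2 also says that all recorded AEs will be listed and tabulated, which could be read as covering everyone. That sentence sits under the statement restricting all safety analyses to the Treated Population. Section 10.3 leaves selection of participants to a separate SAP, which could correct the rule, but the text available states no exception.

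Two points stand. First, data capture is not the problem. The screen-failure information in section 6.4 names SAEs but not non-serious AEs; it is a minimum, and section 9.2.3 requires all identified non-serious AEs to be recorded. Second, Table 2-1 schedules no laboratory, ECG or vital-sign assessments in the run-in column, so a run-in summary can cover AEs only.

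**Conclusion.** The concern holds. As written, the safety set for the background-therapy objective is conditioned on receipt of another drug, and some exposed participants are left out. This is a wrong rule rather than a missing detail, and it should be corrected before database lock.

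The size is unknown and may be zero. The figures above rest on assumed counts and mostly on the worst case, in which every early leaver had an event. What they show is that with 15 per arm, a single omitted case separates no events observed from an event observed.

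The consequence is limited to descriptive summaries in Arms 1 to 3. Run-in AEs in participants who go on to BMS-986141 can still be summarised. The primary endpoint, the sample size, SAE collection and reporting from consent, and Arm 4 are unaffected. No safety test is planned, so no inference changes.

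**What to change.** - Add a Safety Population to section 10.2: all participants who received at least one dose of ticagrelor, aspirin or BMS-986141 given in the study. State explicitly that run-in doses count.
- Use it for the background-therapy safety summaries, by period with a separate denominator for each: run-in (AEs only); Day 1 background dose to BMS-986141; after BMS-986141. Do not pool the periods, because run-in participants are observed for at least 7 days and the others for about 2 hours before BMS-986141.
- Keep the existing Treated Population for analyses after BMS-986141, and amend section 10.3.2 to say which set applies where.
- Report by arm how many left before BMS-986141, with reasons.
- Note as a limitation that participants already established on these drugs may be selected for tolerance. No population definition removes this.

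The cost is one row in the populations table, a few AE tables and a disposition summary, all from data already collected. No visits or participants are added.
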